3.0 Objectives

3.1 Primary Objectives

- 3.1.1 To assess whether treatment with IMPT results in longer time to cognitive failure compared with IMRT. Cognitive failure is defined as the first cognitive failure on any of the following six cognitive outcome variables: Hopkins Verbal Learning Test Revised (HVLT-R) Total Recall, HVLT-R Delayed Recall, HVLT-R Delayed Recognition, Controlled Oral Word Association (COWA), Trail Making Test (TMT) Part A or Part B.
- 3.2 Secondary Objectives
 - 3.2.1 To determine local control in the brain post radiation treatment.
 - 3.2.2 To determine overall survival in each treatment arm.
 - 3.2.3 To assess quality of life measured at two month intervals for a total of two years post-radiotherapy for both treatment arms.
 - 3.2.4 To assess the pattern of cognitive change in memory at two month intervals for two years post-treatment as well as executive function and processing speed.
 - 3.2.5 MRI diffusion weighted images (DWI) and reconstructed apparent diffusion coefficient (ADC) maps will be analyzed to see if there is a difference between pre- and post-treatment scans. These will also be analyzed for differences between the two treatment modalities.
 - 3.2.6 To evaluate if diffusion tensor imaging (DTI) correlates to the cognitive changes and if there are differences between the two treatment modalities.
 - 3.2.7 To assess the pre-treatment factors of recursive partitioning analysis (RPA) class and mini mental status examination (MMSE) in the predictive determination of local and distant control and cognitive outcome in each treatment arm.
 - 3.2.8 To assess the correlation between location of primary lesion, total volume of intracranial disease, and cognitive outcome in each treatment arm.
 - 3.2.9 To determine the relationship between MGMT promoter methylation status and cognitive and local control outcomes.
 - 3.2.10 To document and descriptively compare post-treatment adverse side effects between the two treatment arms.
 - 3.2.11 To determine the relation between dosimetric parameters and cognitive and local control outcomes.
- 3.3 Correlative objectives
 - 3.3.1 To determine if Apo E (i.e., Apo E2, Apo E3, and Apo E4) genotyping may prove to be a predictor of radiation induced neurocognitive decline (or neuro-protection).
 - 3.3.2 To determine if inflammatory markers (i.e., IL-1, IL-6, and TNF- α) may prove to be predictors of radiation induced neurocognitive decline.

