- 10.2.4 At each two month interval follow up visit out to 2 years all six prespecified cognitive test variables will be assessed. The pattern of cognitive change in memory, executive function, and processing speed will be assessed at each time point. The composite cognitive function

score will be determined by averaging standardized Z-scores from all pre-specified cognitive test variables (5 out of 6 are required to calculate a composite score).

- 10.2.5 MRI imaging including diffusion weighted images (DWI) and reconstructed apparent diffusion coefficient (ADC) maps will be analyzed for differences between pre- and post-treatment scans. They will also be analyzed for differences between the two treatment modalities.
- 10.2.6 Diffusion tensor imaging (DTI) will be analyzed for correlation to the cognitive changes and for differences between the two treatment modalities.
- 10.2.7 Pre-treatment factors of RPA class and MMSE will be assessed for predictive determination of local and distant control and cognitive outcome in each treatment arm.
- 10.2.8 Assessment will be made for correlation between location of primary lesion, total volume of intracranial disease, and cognitive outcome for each of the treatment arms.
- 10.2.9 The relationship between MGMT promoter methylation status and cognitive and local control outcomes will be assessed.
- 10.2.10 Post treatment side effects will be recorded at each follow up visit out to two years. Toxicity will be recorded according the Common Terminology Criteria for Adverse Events v4.0.3 for Nervous System Disorders. Only grade 3 and above toxicity that is directly related to therapy will be required to be documented. Pretreatment symptoms should not be considered as toxicity related to the treatment and are not required to be documented unless the symptoms worsen as a result of therapy.
- 10.2.11 Dosimetric parameters such as dose to the hippocampus will be analyzed for relationship with cognitive and local control outcomes.
- 10.3 Evaluation of correlative markers
 - 10.3.1 Genetic markers: DNA will be extracted within the first five fractions of treatment in the laboratory of the Study Chair. Apo E (i.e., Apo E2, Apo E3, and Apo E4) genes will be analyzed for single nucleotide polymorphisms (SNPs) either by Taqman or direct sequencing.

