We will use descriptive statistics to summarize by treatment arm the quality of life data at each assessment time. We will also use boxplots to summarize the quality of life data by treatment arm at each assessment time. We will model the quality of life data using mixed effects regression methods with repeated measures. The model will include treatment arm, selected dosimetric parameters, baseline cognitive function, location of the primary tumor (left vs. right hemisphere, if bilateral disease is present, location will be determined by the hemisphere with highest burden of disease), and the stratification factors used at randomization as fixed effects and patient as a random effect. We will similarly analyze the cognitive tests. For nearly all the prior mentioned analyses we will also plan to conduct an as-treated analysis.

We will tabulate by treatment arm the adverse events by grade and relationship to treatment.

We will use logistic regression methods to model the logit of the probability of neurocognitive decline as function of ApoE (i.e., Apo E2, Apo E3, Apo E4) genotyping, inflammatory markers (i.e., IL-1, IL-6, TNF- α), and hormone growth factors (i.e., glucocorticoids, gonadal steroids, growth hormone, human chorionic gonadotrpin, insulin-like growth factor-1, neuronal growth factor).

Determination of MCP class will be determined by RPA analysis using results of MGMT, *IDH1*, G-CIMP, and mRNA assays as well as RTOG RPA class. We will use descriptive statistics to report class distributions overall and by treatment arm. Survival by classes will be visualized on Kaplan/Meier plots, compared by the logrank test. The Cox proportional hazards regression will be used to model MCP classification, adjusting for treatment arm and stratification factors.

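### The mixed models in 12.4 list no visit or arm-by-visit term, and the quality-of-life model omits the baseline quality-of-life score

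*Combined protocol and SAP*

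**What the plan says.** Section 12.4 introduces the quality-of-life model with "We will model the quality of life data using mixed effects regression methods with repeated measures". The covariates follow: "The model will include treatment arm, selected dosimetric parameters, baseline cognitive function, location of the primary tumor" (left or right hemisphere, with a rule for bilateral disease), "and the stratification factors used at randomization as fixed effects and patient as a random effect". The cognitive outcomes are then covered in one sentence: "We will similarly analyze the cognitive tests". No visit, time or arm-by-visit term appears in this list or elsewhere in the document, and no baseline quality-of-life score is named.

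Before the model, 12.4 plans a description by visit: "We will use descriptive statistics to summarize by treatment arm the quality of life data at each assessment time", together with boxplots by arm and assessment time.

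The objectives these analyses serve concern repeated assessment over two years. For quality of life, 3.2.3 reads: "To assess quality of life measured at two month intervals for a total of two years post-radiotherapy for both treatment arms". For cognition, 3.2.4 reads: "To assess the pattern of cognitive change in memory at two month intervals for two years post-treatment". Section 10.2.4 adds: "The pattern of cognitive change in memory, executive function, and processing speed will be assessed at each time point". The same section defines a composite cognitive score averaged over the test variables. The pretreatment battery in 8.2 includes the MDASI-BT and the EORTC QLQ C30/BN20, so a baseline quality-of-life score is collected.

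**The concern.** A repeated-measures model with an arm term but no time term estimates a single number: the arm difference averaged over whatever visits each patient completed. It gives no trajectory and no arm contrast at a given visit. Objective 3.2.4 and section 10.2.4 ask for the pattern of cognitive change, so the planned model does not answer the planned question. A late benefit, an early cost that resolves, or arms that cross would be averaged together.

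There is also a route to bias. Patients leave follow-up through progression and death. If one arm is followed longer, it contributes more late visits. A decline common to both arms then appears partly as an arm effect, because the model has nowhere else to put it.

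The third issue is precision, and it concerns the quality-of-life model. The best available predictor of a follow-up score is usually the same scale at baseline. That score is collected, but the listed baseline covariate is cognitive function.

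**Working it through.** **Inputs.** From 12.2: 60 evaluable patients, 30 per arm. From 9.1 and 3.2.3: two-monthly visits for 24 months, so 24/2 = about 12 scheduled follow-ups. From 12.4: a patient random effect, which as a random intercept implies compound symmetry. Assumed, because the documents give no value: a correlation rho of 0.3 to 0.7 between any two scores of one patient, baseline included.

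**The plan's own figure.** The document gives no power or precision figure for these models. Its only sizing figure is the 43 events for the primary endpoint. That reproduces: HR = ln 0.70 / ln 0.55 = 0.597, and the Schoenfeld formula at one-sided 0.20 and 80% power gives 43 events (power 80.3%). It does not bear on this point.

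**Step 1: what the listed terms estimate.** With m follow-up visits and no time term, the arm coefficient is the mean of the m visit-specific differences. A 200-replicate random-intercept simulation (30 per arm, 6 visits, rho 0.5, complete follow-up) let the arm difference run from -0.5 to +0.5 SD across visits. The arm-only model gave a mean arm effect of -0.01 SD. A model with baseline, linear time and arm-by-time gave a mean slope difference of 1.01 against a true 1.0, with p < 0.05 in 99% of runs.

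Section 12.4 also does not say whether the baseline score is itself one of the repeated outcomes. If it is, one of the m + 1 averaged differences is zero in expectation and the arm effect is diluted by m/(m + 1): 2/3 = 0.67 with two follow-up visits, 6/7 = 0.86 with six.

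**Step 2: drift.** If every patient in an arm completes n visits, the mean visit index is (n + 1)/2. With a common change of d points per visit and no true effect, the arm-only estimate is d times the difference in mean index. As an illustration with invented inputs (2 points lost per visit, 5 visits against 4): (3.0 - 2.5) x 2 = 1 point. With equal follow-up it is zero.

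**Step 3: baseline adjustment in the quality-of-life model.** In units of the score variance, with no other covariates, the variance of a patient's follow-up mean is

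- without baseline: V0 = (1 + (m - 1)rho)/m
- with baseline: V1 = V0 - rho^2

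The variance of the arm contrast is multiplied by V1/V0:

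| Follow-up visits | rho 0.3 | rho 0.5 | rho 0.7 |
|---|---|---|---|
| 1 | 0.91 | 0.75 | 0.51 |
| 6 | 0.78 | 0.57 | 0.35 |
| 12 | 0.75 | 0.54 | 0.32 |

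Worked case, m = 6 and rho = 0.5: V0 = 3.5/6 = 0.583 and V1 = 0.583 - 0.25 = 0.333. The standard error of the arm contrast falls from sqrt(2 x 0.583/30) = 0.197 SD to sqrt(2 x 0.333/30) = 0.149 SD, as if 30 patients per arm were about 52.

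**The case against.** The strongest reply is that the list is incomplete rather than exclusive. The text says what the model will include, not that it includes nothing else, and calling it a repeated-measures analysis may imply a time factor. An analyst could add one and stay within the wording. That is possible, but the list goes as far as assigning a hemisphere in bilateral disease. A plan that specific should not leave its time term to inference.

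Three stronger readings are tempting, and the documents do not support them.

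- A reader might infer that the plan cannot show change over time at all. It can, descriptively: quality of life is summarised and box-plotted by arm at each assessment, and the instruction to treat the cognitive tests similarly could extend those displays to them. What is missing is model-based inference. Also, 3.2.3 asks only that quality of life be assessed at intervals, so the argument from pattern of change rests on 3.2.4 and 10.2.4, which concern cognition.
- A reader might infer that the cognitive models lose the same precision. They do not lack a baseline: baseline cognitive function is in the list carried over to them. The open question is whether this means the same test's score or the composite.
- A reader might take the drift calculation as evidence of a bias of known size. Its inputs are invented, the scale is unspecified, and the documents do not predict different follow-up lengths by arm. It shows the mechanism only.

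Two further cautions stand. The variance factors ignore covariates already in the model (baseline cognition, MMSE stratum, RPA class, age), so the real gain may be smaller. And visit terms correct for the mix of visits but do not settle informative dropout from progression or death.

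**Conclusion.** The point holds for both models on time, and for the quality-of-life model on baseline. As written, each model yields a visit-averaged arm difference, cannot test the pattern named in 3.2.4 and 10.2.4, and would absorb common drift if follow-up differed by arm. Omitting the baseline quality-of-life score forgoes a variance reduction of 9% to 49% with one follow-up visit and 22% to 65% with six (one minus the factors above). Those ranges depend on an assumed rho of 0.3 to 0.7, compound symmetry and no other covariates. For the cognitive models the baseline covariate is present but undefined. No size can be given for the drift bias from the documents. All of this concerns secondary analyses: the primary endpoint, its Fine and Gray analysis and the sample size are untouched.

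**What to change.** In 12.4:

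1. Add visit and arm-by-visit to both the quality-of-life and the cognitive models. Use categorical visit, or a simpler time form where late visits are sparse.
2. Add the baseline value of the same scale as a covariate in the quality-of-life model, and say that baseline is not also a repeated outcome.
3. In each cognitive model, define baseline cognitive function as the same test's baseline score.
4. Name the visits at which arm contrasts will be reported.

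The cost is SAP wording; no new data are needed. Categorical visit over all 12 follow-ups would add 11 visit and 11 interaction terms, 22 in all, against 2 for linear time. With about 30 evaluable patients per arm the late-visit cells will be thin, which is the reason to allow the simpler form. Dropout through progression or death still needs its own treatment.

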- 12.3 Primary Analysis: The analysis will be performed on the intention-to-treat principle. Considering those patients who are not evaluable as treatment failures. We will use the methods of Gooley et al. [52]to estimate the cumulative incidence of cognitive failure in each treatment arm, considering progressive disease and death before cognitive failure as competing events. We will estimate the cumulative incidence of cognitive failure at 4 months with 95% confidence intervals. We will use the methods of Fine and Gray [53]to test for a difference between treatment arms with respect to the cumulative incidence of cognitive failure, considering progressive disease and death before and death before and death before cognitive failure as competing events. We will use the methods of Fine and Gray [53]to test for a difference between treatment arms with respect to the cumulative incidence of cognitive failure, considering progressive disease and death before cognitive failure as competing events. Our model will include treatment arm and the stratification factors used at randomization.
- 12.4 Secondary Analysis:

We will repeat the primary analysis on only those patients considered evaluable. All the secondary analyses described below will be performed using all patients as well as using only evaluable patients. We will estimate the cumulative incidence of local failure using the methods of Gooley et al. considering death as a competing event. We will model the time to local failure using the methods of Fine and Gray to test for differences between treatment arms, considering death as a competing event. Our model will include treatment arm and the stratification factors used at randomization, as well as selected dosimetric parameters. We will similarly analyze time to distant failure.

We will use the product limit estimator of Kaplan and Meier [54] to estimate overall survival stratified by treatment arm. We will also use Cox proportional hazards regression [55] to model overall survival as a function of treatment arm and the stratification factors used at randomization.

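### Section 12.4 adjusts the arm comparison of QOL and cognitive scores for unnamed, post-randomisation dose measures, so the arm coefficient is not the randomised IMPT-versus-IMRT difference; the local- and distant-failure models share this structure

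*Combined protocol and SAP*

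**What the plan says.** The quality-of-life model in 12.4 is a repeated-measures mixed model: "The model will include treatment arm, selected dosimetric parameters, baseline cognitive function, location of the primary tumor". The stratification factors are further fixed effects and patient is the random effect. The cognitive scores follow the same route: "We will similarly analyze the cognitive tests".

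The local-failure model has an explicit comparative purpose: "We will model the time to local failure using the methods of Fine and Gray to test for differences between treatment arms". Its covariates are given next: "Our model will include treatment arm and the stratification factors used at randomization, as well as selected dosimetric parameters". Distant failure is treated alike: "We will similarly analyze time to distant failure".

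Two sets of variants are announced: "All the secondary analyses described below will be performed using all patients as well as using only evaluable patients", and "For nearly all the prior mentioned analyses we will also plan to conduct an as-treated analysis".

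No section lists the dose measures. Section 10.2.11 offers hippocampal dose as an example, for cognition and local control only.

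Two other models make the contrast. The primary model in 12.3 contains arm and stratification factors only. The Cox model in 12.4 is "to model overall survival as a function of treatment arm and the stratification factors used at randomization".

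**The concern.** Achieved dose is a consequence of assignment. Sections 7.4 and 7.5 have each patient planned after randomisation, in a planning system specific to the assigned modality. Sections 1.0, 4.0 and 5.1 present lower normal-tissue dose as the route by which protons may improve cognition. A model holding both arm and dose removes from the arm coefficient whatever part of the effect travels through dose.

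The remainder is also no longer protected by randomisation. Anything that drives both dose and outcome within an arm can shift it. Disease volume is one candidate: objective 3.2.8 treats its relation to cognition as an open question, and it is not in the model.

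The Abstract gives the comparison of cognition, quality of life and local control between the two modalities as the study's purpose. If brain sparing works as hypothesised, the only regression specified for the repeated scores could show little or no arm difference, or a distorted one, and a reader could take it for the randomised result.

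**Working it through.** **The plan's figures.** Section 12.4 states no effect size, SD, dose separation or power for these models, so there is no figure to reproduce. The primary-endpoint figure does reproduce: HR = ln(0.70)/ln(0.55) = 0.597, and events = 4 × (0.8416 + 0.8416)² / (ln 0.597)² ≈ 42.5, rounded up to the stated 43. The present point does not depend on it.

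**Is there a dose-free arm model for these scores?**
- All versus evaluable patients changes the population, not the covariates.
- As-treated changes the grouping, not the covariates.
- The by-visit summaries and boxplots for quality of life are dose-free but descriptive.
- The biomarker logistic model lists no arm term.

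None is specified.

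**What the arm coefficient estimates.** Take one dose term with within-arm SD 1, and let a lower score be better:
- dose D = −δ·arm + U, where δ is the separation between arms in SD;
- score = −0.60(1 − p)·arm + (0.60p/δ)·D + noise, where p is the share of the effect acting through dose;
- c = covariance of U with the noise, produced by a factor that affects both.

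Without D, the arm coefficient is −0.60(1 − p) − 0.60p = −0.60 for every p. With D, the noise contributes c·U = c(D + δ·arm), so

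arm coefficient = −0.60(1 − p) + c·δ.

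Every input is assumed. c = ±0.09 corresponds to a factor correlating 0.3 in size with both dose and score noise (0.3 × 0.3).

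| Share p | c = 0 | c = +0.09, δ = 1 / 2 / 3 | c = −0.09, δ = 1 / 2 / 3 |
|---|---|---|---|
| 0% | −0.60 | −0.51 / −0.42 / −0.33 | −0.69 / −0.78 / −0.87 |
| 25% | −0.45 | −0.36 / −0.27 / −0.18 | −0.54 / −0.63 / −0.72 |
| 50% | −0.30 | −0.21 / −0.12 / −0.03 | −0.39 / −0.48 / −0.57 |
| 75% | −0.15 | −0.06 / +0.03 / +0.12 | −0.24 / −0.33 / −0.42 |

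For example, −0.60 × 0.25 + 0.09 × 3 = −0.15 + 0.27 = +0.12.

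**Check by simulation with repeated measures.** Assumptions: 30 per arm, up to 6 visits, 0.12 dropout per visit, between-patient variance 0.6, residual variance 0.4, 4,000 replicates per cell. Without dose, the arm estimate was −0.59 to −0.60 throughout. With dose, at δ = 1/2/3:
- p = 50%, c = 0: −0.302 / −0.302 / −0.305
- p = 50%, c = +0.09: −0.209 / −0.119 / −0.032
- p = 75%, c = +0.09: −0.058 / +0.035 / +0.121

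**Local failure.** Targets, expansions and prescription are common to both arms (7.3, 7.5), so dose is taken as unrelated to failure. The arm SE is then multiplied by √(1 + δ²/4) in large samples: 1.00, 1.03, 1.12, 1.41 and 1.80 at δ = 0, 0.5, 1, 2 and 3. For δ = 3 this is √(1 + 9/4) = 1.80. A Cox simulation with an assumed HR of 0.67, 30 per arm and about 40 events gave 1.03, 1.07, 1.20, 1.52 and 1.87. It did not simulate competing death. Across all runs, including 45 per arm, the mean log HR lay between −0.395 and −0.452 with and without the dose term, against a true ln(0.67) = −0.400.

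**The case against.** The strongest reply is that the damage depends on a choice not yet made: a dose measure that barely differs between arms leaves the arm coefficient close to the randomised difference. That is true of the size. It does not rescue the plan, because the one example offered, hippocampal dose, is a brain-sparing measure, and leaving the list open makes the arm estimate depend on a later selection.

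Cognition also has a formal dose-free arm test already, since the primary endpoint uses the same six test variables (10.1.1). This stands and limits the harm, but time to first failure does not replace the longitudinal pattern that objective 3.2.4 asks for.

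Several other limits stand:
- Dose as the route to quality of life is plausible but not stated in the documents.
- Bias is not shown for local or distant failure, and 12.4 also plans a dose-free cumulative incidence estimate of local failure. The Abstract does not name distant failure; distant control appears in objective 3.2.7.
- Only the local-failure model is expressly an arm test, and no power is claimed for any of these secondary analyses.
- The illustrative inputs are assumed. A shared factor of opposite sign strengthens the adjusted coefficient instead of weakening it, and can exaggerate the benefit. Sign reversal in the table needs 75% mediation, a shared factor and at least 2 SD separation together.

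The mixed-model description also lists no visit or arm-by-visit term. That is a separate gap, which removing the dose terms would not close.

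**Conclusion.** The concern holds. As written, the only regression for quality-of-life and cognitive scores yields an arm coefficient conditional on post-randomisation dose, which is a different quantity from the randomised difference. Even as an equal-dose effect, it is valid only with no unmeasured common cause of dose and outcome, a correct functional form and no arm-by-dose interaction.

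The conclusion about what is estimated rests on the model structure and needs no numerical assumption. The case is firmest for cognition, where the protocol states the dose mechanism, and extends to quality of life by inference. For local and distant failure the point is narrower: the arm test is conditional on dose and may lose precision, but very little if the chosen measures hardly differ between arms.

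The consequences are confined to secondary outcomes. The primary analysis, its repeat in evaluable patients and the survival model are not affected. The change should be made before analysis, but the trial's main conclusion does not hang on it.

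**What to change.** In 12.4, define the arm comparison for quality of life, cognitive scores, local failure and distant failure as a model without dose terms:
- local and distant failure: arm and stratification factors, matching the primary and survival models;
- quality of life and cognitive scores: the same, plus the two planned baseline covariates (baseline cognition and tumour side).

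Report the dose-containing models separately as dose-outcome analyses, with the dose measures named in advance. Those for cognition and local control answer objective 3.2.11; label those for quality of life and distant failure exploratory. State that the arm coefficient in these models is not the randomised comparison.

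The cost is SAP wording. No new data and no change in sample size are needed, and the dose question is still answered in its own models.

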7.0 Treatment Plan

- 7.1 Eligible patients will be randomized in equal numbers to each treatment arm using CORe. Randomization will be stratified using the following factors:7.1.1 RPA class (III or IV vs. V)
 - 7.1.2 Mini Mental Status Examination score (21-26 vs. 27-30)
 - 7.1.3 Age (less than 65 vs. 65 or older)
- 7.2 Following randomization, insurance pre-authorization will be obtained for the specified treatment modality. If a patient's insurance will not cover payment for the assigned treatment arm, that patient will be removed from the study and will be treated off protocol.
- 7.3 Radiation target definition for glioblastoma as follows. GTV defined as tumor cavity and any T1 tumor enhancement. CTV will include GTV + 2 cm margin customized to include FLAIR enhancement (if thought by the radiation oncologist to be tumor) and exclude bone, fascia, and other anatomical barriers. PTV-50 will include CTV + 3-5 mm and will be treated to 50 Gy in 30 fractions. PTV-60 boost volume will include GTV + 3-5 mm and will be treated to 60 Gy in 30 fractions.
- 7.4 For patients randomized to IMRT, treatment will be planned using Pinnacle software system. Planning will be based on non contrast CT images obtained at time of simulation in addition to MRI scan. Treatment will be delivered using linear accelerator. Fractionated radiation will be delivered daily M-F with weekends off for all patients. IMRT plans use a configuration of five to seven isocentric 6-MV photon beams delivered in a step-and-shoot technique. For inverse planning specified dose constraints are given to organs at risk including the brainstem, spinal cord, optic chiasm, optic nerves, and cochlea.

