12.0 Statistical Considerations

- 12.1 Randomization procedure: A stratified block randomization procedure will be used. Randomization will be performed using CORe. The randomization strata are as defined above in section 7.0, and the block size will be 6. Patients who withdraw from the study after randomization, but prior to receiving treatment will be considered a cancel and replaced.
- 12.2 Sample size: With IMRT the cognitive function failure rate at 4 months is 45%, based off of comparative analyses of the cognitive failure rate of RTOG 0614 and compared to the cognitive impairment seen on RTOG 0525; we hope to demonstrate that IMPT can achieve a cognitive function failure rate at 4 months of only 30%. We assume the time to cognitive failure in each treatment arm follows an exponential distribution. A cognitive failure rate of 45% at 4 months then implies a median time to cognitive failure of 4.6 months, while a cognitive failure rate of 30% at 4 months implies a median time to cognitive failure to cognitive failure of 7.8 months.

We will use a 1-sided significance level of 0.20 as suggested by Rubinstein et al. [51]for phase II screening trials. We expect to enroll 2 patients per month, and we will randomize 60 evaluable patients (30 to each treatment arm). We will have 80% power to detect an improvement in cognitive failure at 4 months from 45% in the IMRT arm to 30% in the IMPT arm. We expect to observe 43 events, and the analysis will be performed once we have observed these events. We define evaluable patients as those who have received the assigned treatment *and* completed baseline and at least one follow-up neurocognitive testing. We expect we will need an over accrual of 33% to account for those patients not evaluable. Therefore the target total enrollment sample size is 90 patients to accrue a total of 60 evaluable patients. We expect to observe 43 events, and we expect the trial to take 41 months to observe these events.

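### The model relating radiation dose to cognition codes tumour site only as left or right hemisphere and omits tumour volume, so a tumour effect on later cognitive change can be read as a dose effect

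*Combined protocol and SAP*

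**What the plan says.** Objective 3.2.11 asks how dosimetric parameters relate to cognition and local control, and 10.2.11 gives the leading example: "Dosimetric parameters such as dose to the hippocampus will be analyzed for relationship with cognitive and local control outcomes".

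The only cognitive model with dose in it is the repeated-measures mixed model of 12.4. It is written out for quality of life and then extended to the cognitive tests. Its fixed effects are treatment arm, selected dosimetric parameters, baseline cognitive function, the stratification factors (RPA class, MMSE band and age band, from 7.1) and tumour site, coded as "location of the primary tumor (left vs. right hemisphere, if bilateral disease is present" with a rule for bilateral disease. It has no term for lobe, distance to the hippocampus or tumour volume.

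Site and volume do appear elsewhere. Objective 3.2.8 is "To assess the correlation between location of primary lesion, total volume of intracranial disease, and cognitive outcome in each treatment arm", repeated in 10.2.8. That is a separate analysis by arm. Section 12.4 gives no method for it and does not link it to the dose model.

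On how dose arises, 7.3 states "CTV will include GTV + 2 cm margin customized to include FLAIR enhancement", with a further 3-5 mm for the larger planning volume. The boost volume is the GTV plus 3-5 mm.

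**The concern.** Dose to a brain structure is not randomised. Within each arm it varies with where the tumour lies and how large it is, because the target is an expansion of the tumour. Section 4.0 names the temporal lobe and hippocampus as structures that support memory, and three of the six primary cognitive variables are HVLT-R memory scores. If a temporal or large tumour worsens cognition during follow-up for reasons other than radiation, patients with high hippocampal dose will decline more even when dose does nothing. Hemisphere cannot separate these effects: a left frontal and a left temporal tumour receive the same code.

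Sparing normal brain is the mechanism that sections 1.0, 4.0 and 5.1 put forward for a cognitive benefit of IMPT. A dose-response that really reflects tumour anatomy would appear to confirm that mechanism.

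**Working it through.** **The plan's own figures.** The plan gives no figure for the dose analysis, only the sample sizes it would run on, and these reproduce.
- Hazard ratio from 45% and 30% failure at 4 months under exponential times: ln(0.70)/ln(0.55) = 0.597.
- Events at one-sided 0.20 and 80% power: 4 × (0.8416 + 0.8416)² / (ln 0.597)² = 11.33/0.267 = 42.5, so 43.
- Enrolment: 60/(1 − 0.33) = 89.6, so 90.

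The dose model will therefore have about 60 (evaluable) to 90 (enrolled) patients.

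**What baseline adjustment leaves behind.** Let T = 1 for a temporal tumour, d the site effect on the follow-up score in SD, f the share of d that emerges after baseline, and ρ the baseline-to-follow-up correlation.
- Baseline: B = −d(1 − f)T + e.
- Follow-up: Y = −dT + ρe + noise, with no dose term.
- Substituting for e: Y = ρB − d[1 − ρ(1 − f)]T + noise.

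With ρ = 0.75 (assumed), the site effect remaining after baseline adjustment is 0.25d for f = 0, 0.625d for f = 0.5 and d for f = 1.

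**How much passes into dose.** Assumed inputs: 35% temporal tumours, mean hippocampal dose 45 Gy (temporal) and 20 Gy (other), SD 12 Gy, IMPT 5 Gy lower. The within-arm slope of T on dose is 25 × 0.2275/(625 × 0.2275 + 144) = 5.69/286.2 = 0.0199 per Gy, where 0.2275 = 0.35 × 0.65. For d = 0.5 the spurious dose slope is then about −0.025, −0.062 and −0.099 SD per 10 Gy for f = 0, 0.5 and 1. This ignores the small correlation of baseline score with dose.

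**False-positive rate of the dose term.** Nominal 5%, n = 60, true dose effect zero; arm, hemisphere and baseline score in the model:

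| Site deficit | d = 0.3 | d = 0.5 | d = 0.8 |
|---|---|---|---|
| all present at baseline | 6% | 8% | 9% |
| half emerges later | 11% | 20% | 43% |
| all emerges later | 20% | 44% | 80% |
| any of these, temporal site added | about 5% | about 5% | about 5% |

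A repeat run agreed to within about one percentage point.

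**Second illustration, with volume and the stratification factors.** Temporal site and log-volume each had a correlation of about 0.3 or 0.5 with dose. Each lowered later cognition by 0.1 to 0.3 SD beyond its effect at baseline. Baseline reliability was 1.0 or 0.75. There were 2,000 runs per setting.
- n = 60: false positives 9% to 34% (correlation 0.3) and 17% to 77% (correlation 0.5). The spurious slope runs from −0.06 to −0.33 SD per unit of dose (about 1 SD).
- n = 90: 11% to 50% and 22% to 92%. A larger sample makes the false finding more likely.
- No effect after baseline: 5% to 7%, slope no worse than −0.04.
- No correlation of site or volume with dose: about 5%.
- Site and volume added: slope about 0, false positives 4% to 6%.

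**The case against.** The strongest objection is that the model already holds baseline cognitive function and the MMSE stratum. Baseline testing takes place before radiation or within the first 5 fractions (8.2), so much of what a temporal tumour does to memory is measured there and adjusted for. This stands, and it limits the claim: if the tumour acts only before baseline, the bias is close to zero. It does not dispose of the claim. Section 10.1.1 itself says that progression often causes cognitive decline, testing continues for two years (9.2), and 12.4 does not say that scores after progression are left out of the mixed model.

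It also stands that every input to the illustrations is assumed, that 12.4 speaks only of selected dosimetric parameters (the hippocampus comes from 10.2.11 as an example), and that 3.2.11 asks for a relation, not a causal estimate.

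Four stronger readings are tempting and are not supported:
- That the trial's main result is biased. The Fine-Gray comparison in 12.3 holds only arm and the stratification factors.
- That the plan ignores site and volume. Objective 3.2.8 relates both to cognition; what is missing is their use in the dose model.
- That 7.6 sets no dose constraint for the hippocampus. The row without a constraint has lost its label in the available text, and the argument does not need it.
- That local control is equally affected. That model does read "Our model will include treatment arm and the stratification factors used at randomization, as well as selected dosimetric parameters", with no site or volume, but no calculation was made for it and the point is not extended there.

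**Conclusion.** The concern holds for one secondary, observational analysis. As specified, the dose coefficient for cognition can absorb any effect of tumour site or size on cognitive change after baseline. Two conditions must both be met: site or size must be correlated with dose, which 7.3 makes very likely, and must affect cognition after baseline, which 10.1.1 makes plausible. The documents give no figure for either, so the bias cannot be sized. Under the assumed inputs, false positives at n = 60 range from near nominal (6-9%) to 80%, depending mainly on how much of the deficit emerges late. The conclusion is that a tumour effect can be read as a dose effect, not that it will be.

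**What to change.** In 12.4, state that whenever a dosimetric parameter is fitted to the cognitive tests, the model also includes (a) tumour lobe, temporal versus other, or tumour-to-hippocampus distance, and (b) GTV volume. Report the dose coefficient with and without these two terms, so that the reader can see how far it moves.

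The data are at hand: the GTV is contoured under 7.3, both hippocampi under 7.6, and site and volume are already needed for 3.2.8. The change is wording only.

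The cost is two more covariates with 60 to 90 patients and a wider interval for the dose coefficient. The widening is roughly 1/√(1 − R²), where R² is the share of within-arm dose variance explained by the added terms, before any gain from smaller residual variance. In the second illustration R² = 2 × 0.3² = 0.18 or 2 × 0.5² = 0.50, giving intervals about 10% or 41% wider. That width reflects how little dose varies independently of the tumour.
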